#### 15.1 Sample Size Justification

Data from 36 patients (18 randomized to ATI-450 and 18 to Placebo) provide enough precision to ensure that the expected asymmetric 70% confidence interval for the difference in the proportion of responders will be no wider than 31 percentage points. This level of precision for the planned 70% confidence interval will facilitate development decisions in accordance with the methods of Frewer et al. The estimate of the expected 70% confidence interval assumed that the placebo response rate would be approximately 50% on Day 14. The 50% response rate assumption was obtained from the proportion of patients that were either not hospitalized or hospitalized but not requiring supplemental oxygen on Day 14 from the study of lopinavir-ritonavir in adults with severe COVID-19 (Cao B., et al. NEJM 2020).

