### 15.3 Description of Statistical Methods

#### **Efficacy Analyses**

##### **Primary Efficacy Analysis**

The study is hypothesis generating. The primary assessment of efficacy for this study will be the point estimate and corresponding asymmetric 70% confidence interval for the difference in proportions of responders between the ATI-450 and Placebo groups. All subjects who are alive, free of respiratory failure (do not require supplemental oxygen) by Day 14 of the trial will be considered responders. The point estimate and corresponding 70% confidence interval will be derived using a logistic regression model that includes treatment group, baseline age group (<60 versus  $\geq 60$ ), and gender as factors.

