Sample Size Justification

Data from 20 patients (10 randomized to ATI-450 and 10 to Placebo) provide some preliminary information about the efficacy and safety of ATI-450. No hypothesis will be formally tested. The mean and exact 90% confidence intervals for within-group event rates will be estimated and no between group difference will be estimated.

Randomization and Blinding

Prior to the start of the study, the University of Kansas Medical Center will generate a list of randomization numbers that shall be transmitted to the assigned clinical packaging organization for study medication labeling. The randomization list will be stored with access limited to designated personnel for study medication labeling. The randomization list will be made available, as appropriate, to unblind the database.

In the treatment period, subjects will be assigned to 1 of the 2 treatment groups in a random manner and at a 1:1 ratio stratified by baseline age group (<60 versus \geq 60). At the Day 1 visit an investigational center staff member will assign study medication to eligible subjects by selecting an appropriate Subject Kit. The staff member must select Subject Kits in chronological sequence and in an ascending numerical order starting with the lowest available Subject Kit number. No Subject Kit number may be omitted or reused. The Subject Kit number is the randomization number.

This study uses a double-blind design. The study medications are indistinguishable in appearance, as packaged and labeled.

Analysis populations

- The Full Analysis Set (FAS) will include all patients who have been administered at least one dose of study medication. The FAS will be population used in the primary efficacy analysis. The FAS will also be the population used secondary efficacy analyses and summaries as well as the population used in all safety summaries. The FAS will be analyzed/summarized as randomized when applied to efficacy endpoints. The FAS will be analyzed/summarized as treated when applied to safety endpoints.
- The Per-Protocol population will include all FAS patients who have completed their Day 14 visit and have continued study drug administration through Day 14 or were successfully discharged prior to Day 14. The Per-protocol population will be used for the primary efficacy analysis. Summaries and analyses using the per-protocol population will be done as treated.

Statistical Analysis Methods

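### The protocol's 31-point ceiling on the 70% interval at 36 patients does not hold if ATI-450 responds like placebo; it rests on an active-arm rate, interval method and tail levels that are not stated

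*Protocol*

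**What the plan says.** Protocol 15.1 (Sample Size Justification), repeated in the Statistical Methodology row of the Protocol Summary, takes 36 patients, 18 per arm. It says this number ensures that the "expected asymmetric 70% confidence interval for the difference in the proportion of responders will be no wider than 31 percentage points". Section 15.1 then gives one input: "The estimate of the expected 70% confidence interval assumed that the placebo response rate would be approximately 50% on Day 14". It states no ATI-450 rate, no interval formula and no split of the 30% error between the tails. On use, 15.1 says: "This level of precision for the planned 70% confidence interval will facilitate development decisions", with a literature citation but no cut-offs.

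Protocol 15.3 makes the primary assessment the point estimate and "corresponding asymmetric 70% confidence interval for the difference in proportions of responders between the ATI-450 and Placebo groups", "derived using a logistic regression model that includes treatment group", age group and gender. It does not say how the model is turned into an interval for a difference in proportions.

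The SAP differs. It plans 20 patients, 10 per arm, tests no hypothesis, uses exact 90% Clopper-Pearson intervals within each group for the primary endpoint, and states in its sample-size section that no between-group difference will be estimated. The Protocol Summary also lists 20 participants, beside its own sample-size text for 36.

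**The concern.** A statement that a sample size ensures a width no greater than some figure reads as a ceiling. With placebo at 50%, the natural case to check is a drug with no effect, so that both arms are at 50%. That is also where the variance of the difference is largest for this placebo rate. If the ceiling fails there, the precision is overstated in the case where a development decision most needs it.

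Separately, if asymmetric means unequal tails, the one-sided error at the lower limit could be 10%, 15%, 20% or another value. The same data would then give different lower limits, and a split left open could be chosen after the results are seen.

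**Working it through.** **Inputs.** From Protocol 15.1: n = 18 per arm, 70% confidence, placebo rate 0.50, target width 31 points. Assumed because not stated: the ATI-450 rate q (0.50 and above), the lower and upper tail areas a and b with a + b = 0.30, and the interval method.

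**Can 31 be reproduced?** Not from the stated inputs alone. It can with added ones. For example, the expected Wald width at 80% versus 50% with a 20/10 split is 31.0, and so is the expected Agresti-Caffo width at 70% versus 50% with a 15/15 split.

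**Plug-in width at 50% in both arms.** Width = (z(1−a) + z(1−b)) × √[(0.25 + q(1−q))/18]. At q = 0.50 the root is √(0.50/18) = 0.1667.
- 15/15: (1.036 + 1.036) × 0.1667 = 34.5 points
- 20/10: (0.842 + 1.282) × 0.1667 = 35.4 points
- 25/5: (0.674 + 1.645) × 0.1667 = 38.7 points

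For this formula equal tails give the narrowest interval, so no unequal split can bring it down to 31.

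**Expected width.** Section 15.1 speaks of the expected interval, so the closer check averages the width over all binomial outcomes (in points):

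| ATI-450 vs placebo | Split | Wald | Newcombe | Agresti-Caffo |
|---|---|---|---|---|
| 50% vs 50% | 15/15 | 33.6 | 32.7 | 32.0 |
| 50% vs 50% | 20/10 | 34.4 | 33.3 | 32.8 |
| 50% vs 50% | 25/5 | 37.6 | 35.8 | 35.8 |
| 70% vs 50% | 15/15 | 32.2 | 31.5 | 31.0 |
| 70% vs 50% | 20/10 | 32.9 | 31.5 | 31.7 |
| 80% vs 50% | 15/15 | 30.3 | 29.9 | 29.6 |
| 80% vs 50% | 20/10 | 31.0 | 29.7 | 30.3 |

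For 15/15 and 20/10 tails the excess over 31 at 50%/50% is 32.0 − 31 = 1.0 to 34.4 − 31 = 3.4 points. A continuity-corrected Wald interval is far wider (44.7 or more).

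**ATI-450 rate that gives 31.** By expected width, about 70% to 80% for 15/15 and 20/10 tails. By the plug-in formula, about 81% (15/15) or 84% (20/10). A 25/5 split needs about 92% by plug-in.

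**The planned adjusted model.** Logistic regression with treatment, age group and gender, converted to a risk difference by standardisation with a delta-method standard error, was simulated at 50%/50% with 3,000 trials per setting. Mean widths for 15/15 and 20/10 are:
- 33.5 and 34.3 if the covariates carry no information
- 32.5 and 33.3 if each has a log odds ratio of 0.7
- 30.3 and 31.0 if each has a log odds ratio of 1.4 (odds ratio e^1.4 ≈ 4.1)

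**Effect of the tail split.** The lower limit is d − z(1−a) × SE. Take 12/18 versus 9/18: d = 3/18 = 16.7 points and SE = √[(0.667 × 0.333 + 0.25)/18] = 16.2 points.
- 20% lower tail: 16.7 − 0.842 × 16.2 = +3.0
- 15%: 16.7 − 1.036 × 16.2 = −0.1
- 10%: 16.7 − 1.282 × 16.2 = −4.1

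One more responder removes the sign change: 13/18 versus 9/18 gives +8.9, +5.8 and +1.9.

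**The SAP's interval, for comparison.** With 5 of 10 responders the exact 90% limits are the 5th percentile of Beta(5, 6) and the 95th percentile of Beta(6, 5): 22.2% and 77.8%, a width of about 55.5 points within one arm.

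**The case against.** Five points can be made for the protocol.

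- **Equal rates are not its assumption.** It states only the placebo rate, and 31 is obtainable with an effective drug. A reader might infer that the figure is an arithmetic error. The documents do not support that, because the missing rate could make it correct. What remains is that a width depending on an undisclosed favourable effect is not ensured.
- **The planned interval is covariate-adjusted.** This is fair: the tabulated widths are for unadjusted intervals. But adjustment brings the width to 31 at 50%/50% only with strong effects of both age and gender, and the protocol claims none.
- **Asymmetric may not mean unequal tails.** It may mean limits that are not equidistant from the estimate, as a logistic model would give, or the levels may be fixed in the cited framework, which the documents do not reproduce. That stands, and it is why the term needs defining.
- **Nothing turns on zero.** A reader might infer that a go/no-go decision hinges on the lower limit clearing zero. Neither document sets such a rule, and both call the study hypothesis generating. The sign change is a matter of interpretation and is confined to borderline data.
- **The SAP no longer uses this interval.** This stands in full. No primary result under the SAP depends on the width or the split; the problem lies in the protocol's rationale and its disagreement with the SAP.

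**Conclusion.** The ceiling does not hold as worded. At 18 per arm with both arms at 50%, unadjusted expected widths are about 32 to 34 points (plug-in 34.5 to 35.4) for 15/15 and 20/10 tails, against the stated 31. A width of 31 needs an ATI-450 rate of roughly 70% to 84%, depending on method and split, or strongly prognostic age and gender effects. The shortfall is modest, and it rests on the assumption that ATI-450 responds at about the placebo rate. The undefined interval form is a real gap, but its consequence is limited to borderline results such as 12/18 versus 9/18. This is a correction worth making to the protocol's stated precision. It is not a flaw in the SAP's primary analysis.

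**What to change.** Either of two edits would do.

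1. **Keep the protocol's interval.** In the Summary and 15.1, replace the ensured 31-point maximum with the expected width under stated rates in both arms: about 32 to 34 points at 50%/50%, and about 31 only at a stated ATI-450 rate, which lies at roughly 70% to 84% depending on method. In 15.1 and 15.3, name the interval method and the two one-sided levels; if no unequal split is intended, say two-sided 70% with 15% in each tail.
2. **Align with the SAP.** Withdraw the 31-point statement and give the precision of the exact 90% within-group intervals at 10 per arm, for instance 22.2% to 77.8% if 5 of 10 respond. Revise the primary analysis text in 15.3 and the Summary to match. Only this edit also removes the disagreement on sample size and primary interval.

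Either takes a few sentences and no extra patients. The cost is that the stated precision becomes slightly less favourable under the first edit. Under the second, the comparison of arms is no longer presented as the primary estimate, as the SAP already has it.

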#### 15.2 Study Populations

##### Analysis Populations

- The Full Analysis Set (FAS) will include all patients who have been administered at least one dose of study medication. The FAS will be used for the efficacy analyses and summaries. The FAS will be analyzed/summarized as randomized.
- The Per-Protocol population will include all FAS patients who have completed their Day 14 visit and have continued study drug administration through Day 14 or were successfully discharged prior to Day 14. The Per-protocol population will be used for the primary efficacy analysis. Summaries and analyses using the per-protocol population will be done as treated.

### 15.3 Description of Statistical Methods

#### **Efficacy Analyses**

##### **Primary Efficacy Analysis**

The study is hypothesis generating. The primary assessment of efficacy for this study will be the point estimate and corresponding asymmetric 70% confidence interval for the difference in proportions of responders between the ATI-450 and Placebo groups. All subjects who are alive, free of respiratory failure (do not require supplemental oxygen) by Day 14 of the trial will be considered responders. The point estimate and corresponding 70% confidence interval will be derived using a logistic regression model that includes treatment group, baseline age group (<60 versus  $\geq 60$ ), and gender as factors.

##### **Secondary Efficacy Analyses**

Supportive analyses will be conducted on the secondary efficacy endpoints described in Section 3.5. Categorical variables will be analyzed using a logistic regression like that described for the primary endpoint. In addition to the point estimate and confidence interval for the difference in proportions for categorical endpoints, odds ratios, corresponding confidence intervals and p-values will be provided. For categorical measures that are recorded over time, separate logistic regression analyses will be conducted at each timepoint.

Continuous secondary efficacy endpoints will be analyzed using a mixed model repeated measures MMRM analysis. The MMRM will include factors for treatment, baseline age group, gender, and scheduled timepoint as well as a random effect for patient. Model based means for each treatment group, model based differences between treatment groups will be provided over time as well as their corresponding confidence intervals and relevant p-values.

For time-to-event data, a two-sided stratified log-rank test will be applied. The stratification factor will be baseline age group (<60 versus  $\geq 60$ ). Estimates of the 25th, 75th percentile and the median (50th percentile) will be provided for each treatment group. Kaplan-Meier Curves and corresponding 95% confidence intervals will be provided as well as p-values based on the stratified log-rank test.

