	
endpoint. In addition to the point estimate and confidence interval for the difference in proportions for categorical endpoints, odds ratios, corresponding confidence intervals and p-values will be provided. For categorical measures that are recorded over time, separate logistic regression analyses will be conducted at each timepoint.
 
For continuous secondary efficacy endpoints, a mixed model repeated measures MMRM analysis will be conducted. The MMRM will include factors for treatment, baseline age group, gender, and scheduled timepoint as well as a random effect for patient. Model based means for each treatment group and the difference between treatment groups will be provided as well as corresponding confidence intervals and p-values.
 
For time-to-event data, a two-sided stratified log-rank test will be applied. The stratification factor will be baseline age group (<60 versus <math>\geq</math>60). Estimates of the 25th, 75th percentile and the median (50th percentile) will be provided for each treatment group. Kaplan-Meier Curves and corresponding 95% confidence intervals will be provided as well as p-values based on the stratified log-rank test.
 
Safety Summaries
 
The FAS population will be used for the analysis of safety data (AEs, exposure to study medication, clinical laboratory values, vital signs, and ECG).
 
AEs will be coded with the Medical Dictionary for Regulatory Activities. Treatment-emergent adverse events (TEAEs) are defined as AEs with an onset date on or after the date of first administration of study medication and before the date of last administration of study medication + 30 days. TEAEs will be presented by system organ class and preferred term in frequency tables. Patients with multiple AEs will be counted only once within each preferred term and system organ class. Key patient information for patients with an AE with an outcome of death, patients with SAEs, and patients with an AE leading to discontinuation of study medication will be listed.
 
Laboratory data (hematology, serum chemistry, coagulation, and urinalysis) will be converted to Système International units for reporting and processing purposes. Absolute values and changes from baseline will be presented descriptively. Laboratory data outside study specific reference ranges will be listed. Vital signs and ECG parameters will be presented descriptively

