##### 3.2.2 Secondary Endpoints

What is being measured	Measurement time frame	Measurement Tool
Change in 7 point-ordinal scale	Baseline, Day 3, Day 7, Day 14, Day 28 and follow-up.	Using WHO COVID-19 Ordinal scale measuring: Proportion and time to patients with greater than 2 point improvement on the 7 point categorical scale

Change in oxygen saturation-normalization	Baseline and continuous throughout hospitalization	Peripheral capillary pulse oximeter to measure: SpO 2 /FiO 2 ratio over time, sustainment of normalization in 24 hours, and relative shifts in SpO 2 /FiO 2 categories (<235, between 235 and 315, greater than 315) over time
Need for advanced respiratory care	Baseline and continuous throughout hospitalization	Derived from medical record: time of intubation in the ICU, duration of ICU care in days, duration of overall hospitalization in days
All-cause mortality	Baseline and through d60	Noted in patient medical record
Number and percent of adverse events (AEs) and serious adverse events (SAEs); mean change from baseline lab values, vital signs, and ECG	Baseline through day 14 or at discharge <d14, at d28 ±3, d45 ±3 and d60 ±3 (lab values will be examined up to d45) 	CTCAE v5.0; changes in CBC, CMP, Mg, PT/INR, PTT, GGT, hsCRP, D-dimer, LDH, ferritin, creatine kinase, troponin-i, procalcitonin; standard vital signs measurement with pulse ox; ECG
Proportion of participants with normalization of fever for 24h	Baseline through day 14 or at discharge <d14	Standard daily vital measurement and obtained from patient medical record
Development of new bacterial or fungal infection (AE of Special Interest)	Continuous throughout hospitalization	Noted in patient medical record
Incidence of ARDS  through day 14 or at discharge <d14	From day 1 though day 14 or at discharge <d14	Noted in patient medical record
Change in plasma cytokines IL-1β, IL-6, IL-8 and TNF-α	Baseline, day 3, day 7 (or discharge <d7), day 14 (or discharge >d7 and <d14)	Plasma collected from blood and assayed on Luminex panel performed by KUMC BBV Core

 For clarification, lab values will be collected at baseline, day 3, day 7 (or discharge <d7), day 14 (or discharge >d7 and <d14), at day 28 ±3, day 45 ±3. Vital signs, pulse ox will be collected baseline through day 14 or at discharge <d14, at d28 ±3, d45 ±3 and d60 ±3 (lab values will be examined up to d45)

 ARDS Criteria:

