### 15 STATISTICAL CONSIDERATIONS

Details of the statistical summaries will be provided in the study-specific statistical analysis plan (SAP). Generally, the objectives for this study will be assessed via point estimates and corresponding confidence intervals.

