#### 15.5 Intercurrent Events and Missing Data

An intercurrent event is one that occurs after the first dose of study medication and either precludes the observation of the variable or affects its interpretation. The following is a list of negative intercurrent events related to the primary endpoint:

- Death
- Withdrawal from study
- Intubation and ventilation
- Rescue with a non-protocol specified treatment for cytokine release syndrome

The following is a list of positive intercurrent events related to the primary endpoint:

- Early discharge due to recovery

The patient will be considered a responder if the primary endpoint is missing following a positive intercurrent event. Patients will be considered a non-responder for all observations (missing or not missing) following a negative intercurrent event.

Missing data and intercurrent event imputation will be treated in a similar manner as the primary endpoint for secondary endpoints of a categorical nature. For secondary endpoints of a continuous nature, the last observation prior to the intercurrent event will be carried forward (LOCF) for all positive intercurrent events and the worst observation prior to the intercurrent event will be carried forward (WOCF) for all negative intercurrent events.

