#### 15.6 Multiplicity

This is an early pilot study with a single primary endpoint. All secondary endpoints are considered supportive to the primary. The study is hypothesis generating and not intended to support definitive label claims. Therefore, no measures to control for multiplicity will be implemented in the statistical analyses for this study.

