Descriptive statistics (number of observations, mean (standard deviation) or median (minimum, maximum)) will be provided for continuous variables, and counts and percentages will be presented for categorical variables for each group.

Primary Efficacy Analysis

The study is hypothesis generating. The primary assessment of efficacy for this study will be the point estimate and corresponding exact 90% confidence interval for the proportions of responders for the ATI-450 and Placebo groups. All subjects who are alive, free of respiratory failure (do not require supplemental oxygen) by Day 14 of the trial will be considered responders. The point estimate and corresponding 90% confidence interval will be derived based on sample proportions and the Copper-Pearson CIs for proportions for the two groups (categorical data analysis by Alan Agresti, 3rd edition).

Secondary Efficacy Analyses

Binary variables will be analyzed using the method like that described for the primary endpoint. In addition to the point estimate and confidence interval for the difference in proportions for binary endpoints, odds ratios, corresponding confidence intervals will be provided. For binary measures that are recorded over time, separate analyses will be conducted at each timepoint.

Continuous secondary efficacy endpoints will be analyzed by estimating group means and mean difference and 95% CIs at each time point. Missing data will be imputed with the single imputation methods described above (LOCF or WOCF).

For time to discharge from hospital, estimates of the median (50th percentile) will be provided for each treatment group and Kaplan-Meier Curves will be provided. A two-sided stratified log-rank test will be applied. The stratification factor will be baseline age group (<60 versus ≥ 60).

Exploratory Outcomes Analyses

For all the Cytokines, changes over time (baseline, d7, EOT, d28) will be summarized by descriptive statistics and trajectory plots. Any time point after the end of treatment (EOT) will not be measured.

Safety Summaries

AEs will be summarized using table format based on DSMB requirements (attached).

Missing Data Imputation

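### Protocol 15.3 lists an additive MMRM that cannot give the treatment differences over time it promises; the gap is limited to the protocol text and the secondaries the SAP does not compare

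*Protocol*

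**What the plan says.** Protocol 15.3, Secondary Efficacy Analyses, gives the model for continuous secondary endpoints: "The MMRM will include factors for treatment, baseline age group, gender, and scheduled timepoint as well as a random effect for patient". The next sentence sets the output: "model based differences between treatment groups will be provided over time as well as their corresponding confidence intervals and relevant p-values". The Protocol Summary lists the same terms but promises less: "Model based means for each treatment group and the difference between treatment groups will be provided as well as corresponding confidence intervals and p-values".

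Neither place names a treatment-by-timepoint interaction, a baseline covariate or a covariance structure. Neither says whether baseline is part of the response.

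Protocol 3.2.2 makes SpO2/FiO2 over time and the plasma cytokines IL-1β, IL-6, IL-8 and TNF-α secondary endpoints. The cytokines are measured at baseline and Days 3, 7 and 14, or at discharge.

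The SAP, to which Protocol 15 leaves the detail, contains no MMRM. Its Secondary Efficacy Analyses section says: "Continuous secondary efficacy endpoints will be analyzed by estimating group means and mean difference and 95% CIs at each time point". It lists the four cytokines as exploratory, with descriptive statistics and trajectory plots only, and it does not list SpO2/FiO2.

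**The concern.** The listed terms are all additive, so the treatment effect is constrained to be the same at every visit. The promised output, differences over time, needs a treatment effect that can vary by visit. Visit-specific inference appears to be what the authors wanted: the same section asks for a separate logistic regression at each timepoint for categorical measures.

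A programmer who followed the protocol sentence literally could print a table with a row for each visit, and every row would carry the same difference, standard error and p-value. A reader would take the Day 14 row as the Day 14 effect, when it is an average over all modelled visits. If baseline were left in the response, a visit with zero expected difference under randomisation would be averaged in too.

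**Working it through.** **Inputs from the documents.** Model terms and promised output: Protocol 15.3. Cytokine visits: Protocol 3.2.2. Sample size: 10 per arm (SAP) or 18 per arm (Protocol 15.1). The documents give no effect size, SD, correlation or power for this model, so there is no figure of theirs to reproduce.

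**Step 1: algebra.** Under the listed terms, for a patient in arm *t* (0 or 1) at visit *k*,

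E[Y] = μ + τ·t + age + gender + γ_k.

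The difference between arms at visit *k* is (μ + τ + γ_k) − (μ + γ_k) = τ. The visit term cancels, so the difference is τ at every *k*. There is one hypothesis, τ = 0, and one p-value.

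**Step 2: fitted check.** One simulated trial was fitted with 10 per arm, visits at Days 3, 7, 14 and 28, complete data and a random patient intercept (all values assumed).

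- Without the interaction, every visit gives −0.557 (SE 0.531, p = 0.295).
- With it, the visits give −0.0455, −0.2321, −0.1475 and −1.8021 (p = 0.94, 0.71, 0.81 and 0.004).
- The mean of those four is −2.2272 / 4 = −0.5568, which is the additive estimate.

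With complete data, then, τ is the average of the visit-specific differences.

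**Step 3: size.** Assumptions: post-baseline Days 3, 7 and 14; unit SD at each visit; equal correlation ρ = 0.5; complete data; two-sided 5% test with 2n − 2 = 18 degrees of freedom at n = 10; no covariates.

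- Additive test: it compares patient means over k = 3 visits. Their variance is (1 + 2ρ)/3 = 0.667, so SE = √(2/10 × 0.667) = 0.365.
- Day 14 contrast: SE = √(2/10) = 0.447.
- Noncentrality is effect / SE. The additive test uses the mean effect over visits, and the contrast uses the Day 14 effect.
- Coverage of the Day 14 effect by the additive 95% interval is 1 minus the rejection probability at noncentrality |Day 14 effect − mean effect| / 0.365.

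| Effect at Days 3/7/14 (SD) | Mean | Additive noncentrality | Additive power | Day 14 noncentrality | Day 14 power | Coverage of Day 14 effect |
|---|---|---|---|---|---|---|
| 0 / 0.6 / 1.2 | 0.6 | 1.64 | 34% | 2.68 | 72% | 66% |
| 0.6 / 0.9 / 1.2 | 0.9 | 2.46 | 65% | 2.68 | 72% | 88% |
| 0.8 / 0.8 / 0.8 | 0.8 | 2.19 | 55% | 1.79 | 40% | 95% |

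Over ρ from 0.3 to 0.7 the additive powers run from 41% to 30%, 74% to 57%, and 64% to 47%; the Day 14 column does not change. At 18 per arm and ρ = 0.5 the three pairs are 57% v 94%, 89% v 94%, and 81% v 65%.

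If baseline stayed in the response, the average for the first profile would fall from 0.6 to 1.8 / 4 = 0.45 SD.

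**Step 4: which endpoints remain exposed.**

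| Protocol secondary | In the SAP |
|---|---|
| Change in ordinal scale | Secondary, in the set given visit-wise estimates; not exposed |
| SpO2/FiO2 over time | Not listed |
| IL-1β, IL-6, IL-8, TNF-α | Exploratory, descriptive only |

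For the last two rows the protocol's MMRM is the only between-group method that names a model.

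**The case against.** The strongest reply is that the SAP has dealt with this. The protocol defers analysis detail to it, and its method for continuous secondary endpoints is a mean difference with 95% CI at each time point. No SAP analysis uses the MMRM. A reader might infer that the trial's continuous secondary results will be wrong by visit, and the documents do not support that. What stands against the reply is narrow: the SAP does not say that it supersedes the MMRM, and it gives no between-group comparison for the four cytokines or, by name, for SpO2/FiO2. Making the cytokines descriptive may have been deliberate.

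Second, the word include does not rule out an interaction, and the promise of differences over time hints at one. That is fair: the model is under-specified, not shown to exclude the term. The Summary promises only the difference between groups, so it has no internal conflict.

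Third, the harm depends on the profile. Early effects are plausible: Protocol 1.1.4.4 reports near steady state by Day 2. With 0.8/1.0/1.2 SD the additive test has 74% power against 72%, so the loss disappears. A reader might also reach for a worse case by adding a null Day 28 visit (0/0.6/1.2/0 SD gives 23% v 72%, with 48% coverage of the Day 14 effect). Protocol 3.2.2 does not list Day 28 for the secondary cytokines, although 14.1.2 does collect blood then. For the ordinal scale, which has Day 28, the stated measures are a proportion and a time to improvement, not a mean.

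Finally, Protocol 15.6 says "All secondary endpoints are considered supportive to the primary", and the SAP tests no hypothesis formally. Power therefore carries little weight here.

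**Conclusion.** The point holds as a minor one. As listed, the model in Protocol 15.3 cannot produce the visit-specific differences that the section promises. It produces one time-averaged difference and one p-value, the same at every visit. It would be wrong to say that the p-value tests a different hypothesis at each visit: it tests a single one, that the common effect is zero, and does not address the visit-specific difference.

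The algebra needs no assumption beyond the listed terms. The equality with the average of visit differences needs complete data, which the carry-forward rules in Protocol 15.5 approach but do not guarantee.

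The practical size is not fixed by the documents. Under the stated assumptions it runs from a loss of 38 points of power (34% v 72%) to a gain of 15 points (55% v 40%). Intervals labelled Day 14 cover the Day 14 effect 66% to 95% of the time. The scope is the protocol text plus SpO2/FiO2 and the four cytokines, all supportive endpoints in a hypothesis-generating study.

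**What to change.** Preferred: in Protocol 15.3 and the Protocol Summary, replace the MMRM sentences with the SAP's method, the mean difference and 95% CI at each time point. Apply it at post-baseline visits to SpO2/FiO2 and the four cytokines as well. Say in the SAP that this supersedes the MMRM. Settle the cytokine visits at the same time, since the SAP lists baseline, Day 7, end of treatment and Day 28, and the protocol's secondary table lists baseline and Days 3, 7 and 14. If the cytokines are meant to be descriptive only, move them out of the protocol's secondary endpoints and say so.

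If an MMRM is kept, model post-baseline visits only, add treatment-by-timepoint and the baseline value, state how within-patient correlation is handled, and take each visit's difference from the interaction contrasts. Any time-averaged effect should be reported under that name.

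The cost is a short edit in two protocol places and the matching SAP text, with no new data. The drawback is precision: if the effect is constant over visits, a visit-specific estimate has SE 0.447 SD against 0.365 SD for the pooled one under the assumptions above.
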